11.4.3 Handling of missing values/censoring/discontinuations

Patients who discontinue after the 4 week efficacy assessment for any reason will be considered non-responders in the primary analysis (unless their last recorded TSH value was after 8 weeks of treatment and was above the lower limit of the normal range, 0.35 mU/L). Patients who discontinue before 4 weeks of treatment for any reason will be replaced and not counted for the calculation of responders. For total T3 and free T4, the last recorded value will be used for the change from baseline, provided it was obtained after at least 8 weeks of treatment.

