	No study drug taken	Yes
Subjects are excluded from PD analysis in case of these PDs:		
I01	Deviation from inclusion criteria 1 (ICF not obtained)	Yes
	No study drug taken	Yes

Category Deviation code	Text description of deviation	Data exclusion
	Subject took any prohibited medications interfering with efficacy	Yes
Subjects are excluded from PK and PD analysis in case of these PDs:		Exclude subject from PK and PD analysis sets
I01	Deviation from inclusion criteria 1 (ICF not obtained)	Yes
	No study drug taken	Yes

There are two categories of medications which are considered rescue medication. In order to identify these for programming purposes these are included in the protocol deviations dataset with codes of O01 and O02 (oral corticosteroids and anti-thyroid drugs) however they are not protocol deviations so will not be included in the protocol deviations listing, instead they will be included in a separate rescue medication listing.

In PD outputs the following rules will be applied to subjects who received rescue medication

- Data post rescue medication will be flagged in the listings with a * and a footnote added to explain.
- Figures showing individual profiles will appear as red lines from the point at which the rescue medication was taken and a footnote added to explain.
- In summary tables and summary figures datapoints after rescue medication will be excluded and a footnote added to explain.
- In the inferential analyses datapoints after rescue medication will be excluded and a footnote added to explain. For the longitudinal models the model is expected to provide unbiased results under the assumption that the rescue medication intake can be considered dependent only on previously observed values (MAR – missing at random).

If updates to this table are needed, an amendment to the SAP needs to be implemented prior to DBL.

5 Statistical methods for Pharmacokinetic (PK) parameters

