6.1.1 Variables

The effects of CFZ533 on thyroid function will be primarily assessed by the proportion of

patients whose TSH levels normalize (above 0.35 mU/L) after 12 weeks of treatment (TSH responders). They will also be assessed by the difference in mean total T3 and free T4 between baseline (Day 1, predose) and after 12 weeks of treatment, and the proportion of patients whose total T3 or free T4 levels normalize (below ULN) after 12 weeks of treatment.

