6.1.3.1 Handling of missing values/censoring/discontinuations

Patients who discontinue after the 4 week efficacy assessment for any reason will be considered non-responders in the primary analysis (unless their last recorded TSH value was after 8 weeks of treatment and was above the lower limit of the normal range, 0.35 mU/L). Patients who discontinue before 4 weeks of treatment for any reason will be replaced and not counted for the calculation of responders. For total T3 and free T4, the last recorded value will be used for the change from baseline (Day 1, predose), provided it was obtained after at least 8 weeks of treatment.

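### Rescued patients can drop out of the by-visit TSH and T3/free T4 normalisation rates, and one row of SAP Table 4-1 deletes patients whom SAP 6.1.3.1 counts as failures

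*SAP*

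**What the plan says.** **Non-responder rule.** Protocol 11.4.3 and SAP 6.1.3.1 agree: "Patients who discontinue after the 4 week efficacy assessment for any reason will be considered non-responders in the primary analysis". The one exception is "unless their last recorded TSH value was after 8 weeks of treatment and was above the lower limit of the normal range" (0.35 mU/L). For total T3 and free T4 the only rule is that the last value feeds the change from baseline, "provided it was obtained after at least 8 weeks of treatment".

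**Responder outputs.** SAP 6.1.1 adds a variable that Protocol 11.4.1 does not list: "the proportion of patients whose total T3 or free T4 levels normalize (below ULN) after 12 weeks of treatment". SAP 6.1.2 plans TSH responder frequencies at every timepoint and the same for total T3 and free T4. SAP 6.1.3 adds results at week 20.

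**Rescue rules, SAP Section 4.** For descriptive outputs: "In summary tables and summary figures datapoints after rescue medication will be excluded and a footnote added to explain". For tests and models: "In the inferential analyses datapoints after rescue medication will be excluded and a footnote added to explain". A missing-at-random argument is offered, but only for the longitudinal models. Two drug categories count as rescue: "oral corticosteroids and anti-thyroid drugs) however they are not protocol deviations".

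**Table 4-1.** One row removes from PD analysis anyone matching this description: "Subject took any prohibited medications interfering with efficacy". Protocol Table 5-1 lists iodine (including radioactive iodine), methimazole, propylthiouracil, amiodarone and live vaccines as prohibited. Protocol 3.2 names radio-iodine as standard of care. Protocol 6.9 takes patients who receive standard-of-care treatment for worsening disease off the study.

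**The concern.** A patient who needs thyroid treatment during the study is, on its face, a patient whose disease the drug did not control. SAP 6.1.3.1 recognises this by scoring discontinuers as failures. Section 4 works the other way: it drops the data and does not say whether the patient stays in the denominator. Where the non-responder rule does not reach, two programmers could follow the text faithfully and report different rates, and one of those rates would rise as more failures are rescued.

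The missing-at-random argument does not help here. It concerns a model that borrows from earlier visits. A simple proportion among patients with usable data does not do that.

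With about 12 patients each removal is visible. Protocol 3.2 justifies withholding standard of care only for the 12-week treatment period, so rescue may be more common at later visits, where the rule offers least protection.

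**Working it through.** 1. **The plan's own figures.** Inputs from Protocol 11.4.2 and 11.6 and SAP 6.1.3: n = 12, null rate 5%, one-sided 10% exact test, success at 3 or more responders, assumed true rate 38%.
   - P(X ≥ 3 | 12, 0.05) = 0.0196, below 0.10.
   - The exact 80% lower bound for 3/12 is the 10th percentile of Beta(3, 10) = 0.0957, which matches the stated value of about 10%.
   - P(X ≥ 3 | 12, 0.38) = 0.893, which matches the stated power of around 89%.

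2. **Where the non-responder rule reaches.**

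| Output | Status of a patient rescued after week 4 |
|---|---|
| Week-12 TSH test (SAP 6.1.3) | Non-responder if discontinued, subject to the late-TSH exception |
| By-visit TSH responder rates (6.1.2), including week 20 | Not stated; post-rescue data excluded |
| Week-12 total T3/free T4 normalisation (6.1.1) | Not stated; post-rescue data excluded |
| By-visit total T3/free T4 normalisation (6.1.2) | Not stated; post-rescue data excluded |

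   A patient rescued between weeks 4 and 8 has no pre-rescue T3 or free T4 value late enough for the carry-forward rule. In any case, that rule serves the change from baseline and not the proportion.

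3. **Size for the exposed rates.** If k patients, all scored as failures, leave a denominator of n, the displayed rate is x/(n − k) instead of x/n, so it is multiplied by n/(n − k).
   - n = 12: k = 1 gives 12/11 = 1.09; k = 2 gives 12/10 = 1.20; k = 3 gives 12/9 = 1.33.
   - Purely as an illustration, 6/12 = 50% would read 6/10 = 60% with two removed.
   - The documents give no rescue rate, so k is an assumption throughout.

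4. **Week-12 TSH decision.** P(X ≥ 2 | n, 0.05) = 1 − 0.95^n − n(0.05)(0.95)^(n−1).
   - n = 12: 1 − 0.5404 − 0.3413 = 0.118, fails.
   - n = 11: 1 − 0.5688 − 0.3293 = 0.102, fails.
   - n = 10: 1 − 0.5987 − 0.3151 = 0.086, passes.
   - Three responders: P(X ≥ 3 | 22) = 0.0948 passes and P(X ≥ 3 | 23) = 0.1052 fails, so 3 responders pass for every n from 3 to 22.

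   Only a result of exactly 2 responders could change, and only if two or more of 12 patients were removed. For rescue with anti-thyroid drugs this should not happen, because Protocol 6.9 makes the patient a discontinuer and 6.1.3.1 then scores a failure. Oral-corticosteroid rescue is less clear, since no passage explicitly ties it to discontinuation.

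5. **Table 4-1 traced for one patient.** A patient receives radio-iodine at week 9 for worsening disease, with TSH still suppressed. Radio-iodine is prohibited (Protocol Table 5-1) and is not one of the two SAP rescue categories, so the Table 4-1 row removes the patient from PD analysis. It is also standard of care (Protocol 3.2), so Protocol 6.9 discontinues the patient, and 6.1.3.1 scores a non-responder. The same patient is deleted by one rule and counted as a failure by another. Amiodarone followed by discontinuation gives the same result.

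**The case against.** The best case for the plan is that Section 4 excludes datapoints, not patients, so a fixed denominator is still possible. The SAP speaks of frequencies, and its TSH bar chart shows numbers of responders. The T3/T4 charts are described as similar, so they are probably counts too. Counts are not inflated by removing failures. The exclusion is prespecified and footnoted, with a separate rescue listing and individual profiles split by rescue status. The study is non-confirmatory, and the table shells, which are not in these documents, may settle the denominator. It can also be argued that the main clause of 6.1.3.1 covers any discontinuer and that only its exception is specific to TSH.

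Much of this stands, and it is why the finding is that patients can leave the rates, not that they will. It does not close the gap. The main clause is limited to the primary analysis, and SAP 6.1.1 attaches the responder label to TSH. Whether the T3/free T4 proportion is covered is therefore a matter of interpretation, and the by-visit rates are not covered. The Table 4-1 row removes whole subjects, so the datapoint argument does not apply to it.

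A reader might also infer four stronger points that the documents do not support:
- That the late-TSH exception lets a value taken on rescue count as a response. Section 4 already bars post-rescue data from inferential analyses.
- That the Table 4-1 row deletes patients given methimazole or propylthiouracil because the protocol prohibits them. The SAP expressly classes anti-thyroid drugs as rescue and not as deviations.
- That a week-20 responder test could be tipped. SAP 6.1.3 only says that results will be shown at week 20, directly after the t-test sentence, and states no week-20 responder test or decision.
- That the primary success rule is compromised. Step 4 of the working shows that it is largely protected.

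**Conclusion.** The point holds as a minor one. For the by-visit TSH responder rates and the total T3/free T4 normalisation proportions, including any responder rate shown at week 20, it is a gap: Section 4 removes post-rescue data, no denominator is stated, and the non-responder rule does not clearly apply. If rescued patients do leave, a rate based on 12 patients is inflated by a factor of 1.09 to 1.33 for one to three removals. This assumes that every removed patient would otherwise be scored as a failure, and the number removed is not known.

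The Table 4-1 conflict is direct but narrow. It needs a patient who takes a prohibited treatment outside the two rescue categories, such as radio-iodine or amiodarone, and who discontinues after week 4.

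The week-12 TSH decision changes only with exactly 2 responders and at least two of 12 patients removed. No other stated decision rule is affected. Confidence is medium, because the table shells may already resolve part of this.

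**What to change.** Amend the SAP before database lock; Section 4 itself requires an amendment for changes to Table 4-1.

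- Do not apply the prohibited-medication row of Table 4-1 to the responder analyses.
- For every TSH and T3/T4 responder or normalisation rate, at every timepoint, use one fixed denominator: treated patients who completed 4 weeks of treatment and the week-4 evaluations. Count as a non-responder anyone who, before that timepoint, started SAP-defined rescue after the first dose or took another prohibited medication interfering with efficacy. The words on starting after the first dose keep the stable background prednisolone allowed by exclusion criterion 21 from being scored as rescue.
- Keep the post-rescue-excluded summaries as a supportive display, with n shown at each visit.

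The cost is SAP wording and a responder flag; no new data are needed. Rates become slightly less favourable. The rule is conservative in one respect: a true responder given an oral corticosteroid for an unrelated reason would count as a failure.

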5.1 Variables

Corporate Confidential Information

Cmin from the plasma concentration-time data.

In the zz.xpt file in GPSII (merge file), PK concentration (free CFZ533 in plasma) will be expressed in unit 'microg/mL' (in addition to 'nanog/mL'), and time will be expressed in unit 'day' (in addition to 'hours'). Two variables for the elapsed time will be provided: (i) elapsed time since first dose, and (ii) elapsed time since last dose.

The zz.xpt file in GPSII will combine PK output (free CFZ533 in plasma) as well as PD readouts including: free CD40 on blood B cells, total CD40 on blood B cells, total soluble CD40 in plasma, and total soluble CD154 in plasma. Also, for these PD readouts, two variables for the elapsed time will be provided (see above chapter).

Concentrations below the LLOQ will not be considered for PK parameter calculations.

5.2 Descriptive analyses

Corporate Confidential Information

5.2.1 Graphical presentation of results

Corporate Confidential Information

5.2.2 Pharmacokinetics/Pharmacodynamics relationships

Corporate Confidential Information

6 Statistical methods for Pharmacodynamic (PD) parameters

6.1 Primary objective

The primary aim of this study is to assess the effects of CFZ533 on thyroid function, focusing on TSH levels, total T3 and free T4 in GD after 12 weeks of treatment.

6.1.1 Variables

The effects of CFZ533 on thyroid function will be primarily assessed by the proportion of

patients whose TSH levels normalize (above 0.35 mU/L) after 12 weeks of treatment (TSH responders). They will also be assessed by the difference in mean total T3 and free T4 between baseline (Day 1, predose) and after 12 weeks of treatment, and the proportion of patients whose total T3 or free T4 levels normalize (below ULN) after 12 weeks of treatment.

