4.1 Inclusion criteria

Patients eligible for inclusion in this study have to fulfill **all** of the following criteria at screening:

1. Written informed consent must be obtained before any assessment is performed.
2. Male and female patients 18 to 65 years of age included.
 - Women of child-bearing potential must be willing to use the highly effective methods of contraception (definition in Exclusion criteria #24) during the study treatment epoch and for 12 weeks after the last study treatment.

3. Graves' hyperthyroidism ([Baskin et al 2002](#)) with the following labs measured at screening:
 - TSH<LLN and either FT3>ULN or FT4> ULN
4. Patients must weigh at least 40 kg to participate in the study
5. Able to communicate well with the investigator, to understand and comply with the requirements of the study.
6. Patients have received up to date required vaccinations based on local guidelines.

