Study completion information																	X
TSH	X	X	X		X		X		X		X		X	X	X	X	X
Total and free T3 & T4	X	X	X		X		X		X		X		X	X	X	X	X
PK (CFZ533) ⁹			X	X	X	X	X	X	X	X	X	X	X	X	X		X
Free & total CD40 on B cells ⁵				X			X		X		X		X	X	X		X
Soluble CD40 ⁵				X			X		X		X		X	X	X		X
Soluble CD154 ⁵				X			X		X		X		X	X	X		X
Exploratory Biomarkers in Serum ⁶		X	X		X		X		X		X		X	X	X	X	X
Corporate Confidential	X	X	X		X		X		X		X		X	X	X	X	X
Corporate Co	X	X	X		X		X		X		X		X	X	X	X	X
Corporate Confidential Information			X ⁸														
Corporate Confidential Information		X ¹³									X						

¹ Visit structure given for internal programming purpose only

² Only those inclusion/exclusion criteria that are specific for baseline visit

³ Immunogenicity: 0-hour sample is taken **pre-dose**

⁴ Corporate Confidential Information

⁵ On days when patient is dosed, sample is taken **pre-dose** (0-hour)

⁶ Corporate Confidential Information

⁷ Corporate Confidential

Information

Corporate Confidential Information

⁹ 0-hour sample (or assessment) is taken **pre-dose**, 1-hour sample is taken 1 hour **AFTER** the END of infusion

¹⁰PPD or QuantiFERON TB-gold test

Corporate Confidential Information

¹²The baseline visit assessments can be completed on Day 1 (pre-dose) when the first dose (Day 1) is received within 7 days of the screening visit.

¹³These assessments will be completed prior to the study treatment on Day 1 (Visit 101, **pre-dose**) if Day 1 is scheduled within 7 days of the screening visit (Visit 1).

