11.6 Sample size calculation

The proposed sample size for this study is 12 patients (to complete the study). Assuming CFZ533 is associated with 38% normalization of the TSH levels after 12 weeks of treatment (which is consistent with the response rate seen with Rituximab in 26 weeks in one small, open-label study ([Heemstra et al 2008](#)), there is around 89% power to detect a proportion of TSH responders significantly higher than 5% (this would be achieved with at least 3/12 responders), with a type I error of 10%. Additionally, this sample size provides 98% power to detect normalization of the total T3 (and free T4, respectively) below the upper limit of the normal range (2.79 nmol/L and 22.7 pmol/L, respectively). The assumed baseline levels are 7.2 nmol/L for total T3 and 58.55 pmol/L for free T4, which are the average values reported in GD patients in [Andrade et al \(2001\)](#). The assumed standard deviation for the change from baseline are 4.24 nmol/L and 34.58 pmol/L respectively.

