1.4 Study design and treatment

This is a non-confirmatory, open-label, one treatment arm study in patients with newly diagnosed GD.

A total of approximately 15 patients will be enrolled and treated with CFZ533 to ensure approximately 12 completers. For each patient, the study will consist of a screening epoch of up to 28 days, a baseline evaluation, a 12-week treatment epoch, 24-week follow up epoch after the last dosing of CFZ533 on Study Day 85, and a study completion evaluation on Study Day 253. Patients who discontinue the drug before having completed 4 weeks of treatment and 4 week efficacy and safety evaluations will be replaced with a newly enrolled patient. The study design is presented in Figure 1-1.

Figure 1-1 Study design

2 First interpretable results (FIR)

First interpretable results (FIR) will be provided for this trial.

The study FIR template (mock slides) can be found in CREDI in the study RAP folder.

The template shows the analysis / results to be presented in the FIR. Study outputs required to be created at the time of the FIR will be highlighted in TFL shells document and marked as "Key" in the Programming Deliverables Tracker (PDT) output list.

3 Interim analyses

Corporate Confidential Information

4 Statistical methods: Analysis sets

For all analysis sets, patients will be analyzed according to the study treatment received.

All patients that received study drug and with no protocol deviations with relevant impact on safety will be included in the safety analysis set.

The PK analysis set will include all patients with at least one available valid (i.e. not flagged for exclusion) PK concentration measurement, who received any study drug and experienced no protocol deviations with relevant impact on PK data.

The PD analysis set will include all patients with any available PD data, who received any study drug and experienced no protocol deviations with relevant impact on PD data, who have completed at least 4 weeks of treatment with CFZ533.

The analysis sets and protocol deviation codes are related as follows:

Table 4-1 Protocol deviation codes and analysis sets

Category Deviation code	Text description of deviation	Data exclusion
Subjects are excluded from all (safety) analysis in case of these PDs:		
I01	Deviation from inclusion criteria 1 (ICF not obtained)	Yes
	No study drug taken	Yes
Subjects are excluded from PK analysis in case of these PDs:		
I01	Deviation from inclusion criteria 1 (ICF not obtained)	Yes

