6.1.2 Descriptive analyses

TSH levels will be summarized over time together with their changes from baseline. The frequency of TSH responders will be summarized for each timepoint. Same statistical analysis will be performed for the frequency of patients whose total T3 and free T4 levels normalize. Results will also be presented for free T3 and total T4.

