6.1.3 Statistical model, assumptions and hypotheses

One of the main efficacy criteria for this study is to show that the proportion of patients with normalization of TSH (above 0.35 mU/L) after 12 weeks of treatment with CFZ533 is statistically greater than 5%, according to a 1-sided exact test for proportions with a 10% type I error. This will be achieved if we observe at least 3/12 responders since in that case the lower bound of an 80% confidence interval for the proportion of responders will be about 10%. The other efficacy criteria are that there is a significant reduction in average total T3 and free T4 after 12 weeks of treatment, according to a 1-sided paired t-test with 10% type I error for each of these two endpoints. Results will also be presented for free T3 and total T4 and at week 20.

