6.1.3.3 Graphical presentation of results

Mean (SD) TSH levels and Mean (SD) change from baseline in TSH levels will be plotted over time. Overlaying TSH level profiles will also be presented. Similar figures will be presented for total and free T3 and T4. Overlaying profiles will have separate pages for all

subjects, subjects that have received rescue medication and subjects that received no rescue with the time of the start of the rescue medication indicated on the plot.

Bar charts of the number of TSH responders will be plotted over time. Similar bar charts will be plotted for the frequency of patients whose total and free T3 and T4 levels normalize.

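### SAP 6.1.1 counts total T3 or free T4 as normalized on a value below ULN alone, with no Day 1 condition and no lower limit (minor; one descriptive proportion)

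*SAP*

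**What the plan says.** SAP 6.1.1 assesses the primary objective through TSH responders, the mean change in total T3 and free T4 from Day 1 predose, and "the proportion of patients whose total T3 or free T4 levels normalize (below ULN) after 12 weeks of treatment". Day 1 predose is named as baseline for the mean change. No baseline condition is attached to the proportion.

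SAP 6.1.2 summarizes TSH responders at each timepoint and then says: "Same statistical analysis will be performed for the frequency of patients whose total T3 and free T4 levels normalize". It extends the results to free T3 and total T4. SAP 6.1.3.3 adds bar charts and overlaid individual profiles. None of these sections adds to the definition.

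Entry is governed by protocol 4.1, criterion 3: "TSH<LLN and either FT3>ULN or FT4> ULN", measured at screening, which may be up to 28 days before dosing. SAP section 4 defines the PD set as follows: "The PD analysis set will include all patients with any available PD data, who received any study drug", with further conditions on protocol deviations and at least 4 weeks of treatment. It does not require a raised hormone on Day 1.

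The tests are in SAP 6.1.3: an exact test on TSH responders, and for mean total T3 and free T4 a reduction "according to a 1-sided paired t-test with 10% type I error for each of these two endpoints". The T3/T4 normalization proportion is not tested, and protocol 11.4.1 does not list it.

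**The concern.** For TSH a bare threshold works reasonably well. Every entrant must be below LLN at screening, and the SAP treats 0.35 mU/L as the lower limit of normal, so a value above it marks a move out of the abnormal range since screening. SAP 6.1.2 carries the same treatment over to total T3 and free T4, where entry gives no such assurance. Free T4 may be unraised if free T3 qualified the patient. Total T3 and total T4 are not in the criterion at all. Values may also change between screening and Day 1.

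Two kinds of patient therefore meet the written rule without having moved from high to normal: one who was never above ULN on that hormone at dosing, and one whose value has dropped below the normal range. In a single-arm study a reader will tend to take a normalized count as drug effect, and this one can be above zero for reasons unrelated to the drug.

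**Working it through.** **1. What depends on the definition.** Protocol 11.6 describes 98% power to detect normalization of total T3 and free T4. I checked whether that figure is the power of this proportion or of the mean change. Inputs from protocol 11.6: n = 12; baseline means 7.2 nmol/L and 58.55 pmol/L; ULN 2.79 and 22.7; and "The assumed standard deviation for the change from baseline are 4.24 nmol/L and 34.58 pmol/L respectively". The test is a 1-sided paired t-test at 10%, and power is P(noncentral t with 11 df and noncentrality √12 × difference/SD exceeds the 90th percentile of t with 11 df).

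- Total T3: 7.2 − 2.79 = 4.41; 4.41/4.24 = 1.040; noncentrality 3.60; power 98.5%.
- Free T4: 58.55 − 22.7 = 35.85; 35.85/34.58 = 1.037; noncentrality 3.59; power 98.5%.

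The stated 98% is thus the power for the mean change. The definition of the proportion does not enter it.

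**2. Share already below ULN on Day 1.** The documents give no baseline SD, so this step rests on assumptions. I took the baseline SD as f × the SD of change, with f = 0.5, 0.75 and 1. Free T3 was given the same mean/ULN ratio and CV as total T3. Correlation between hormones was 0.5, 0.8 or 0.95. Distributions were either normal with negative values removed, or lognormal with the same mean and SD. Entry required free T3 or free T4 above ULN. One value per hormone served as both the screening and the Day 1 value, so fluctuation between the two is not modelled. There were 2,000,000 draws per setting.

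| Baseline SD | Total T3 below ULN | Free T4 below ULN | Expected number of 12 | P(none of 12) |
|---|---|---|---|---|
| half | under 2% | under 2% | 0.0–0.2 | 81% to over 99% |
| three-quarters | 0.9–6.2% | 0.7–5.3% | 0.1–0.7 | 47–92% |
| full | 2.6–8.8% | 1.9–7.4% | 0.2–1.1 | 33–80% |

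Here P(none of 12) = (1 − p)^12; for example (1 − 0.0878)^12 = 0.33 and (1 − 0.0176)^12 = 0.81. Two or more such patients is at most 2% likely at half SD. It reaches 29% only at full SD with the truncated normal and correlation 0.5.

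Without the entry rule, an untruncated normal at full SD gives Φ(−1.040) = 15% for total T3, or 12 × 0.149 = 1.8 patients. That overstates the problem, because it includes patients whom criterion 3 excludes and allows negative hormone values.

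**3. Effect on the reported proportion.** Each already-normal patient who stays below ULN adds 1/12 = 8.3 points to the count. With three patients who truly move from high to normal and one who was already normal, the written rule gives 4/12 = 33%. With the denominator restricted to patients above ULN on Day 1, the result is 3/11 = 27%. With no already-normal patient, the Day 1 gap has no effect.

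**4. Values below LLN.** The documents give no LLN for total T3 or free T4, so this part cannot be sized. SAP section 4 already excludes datapoints after rescue medication from summary tables and figures. That closes one route to low values, namely antithyroid drugs given as rescue.

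**The case against.** The best defence is the word itself. A value that was normal before dosing does not normalize, and the bracket may only supply the cut-off, as the bracket for TSH does in the same section. The table shells, which are not available here, may settle the rule. This reading is fair, but the SAP text does not state it, and a programmer following the bracket would count the patient.

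The planned outputs may also show the problem. The individual profiles would reveal a patient who starts below ULN, and the hormones are scheduled on Day 1. This stands in part: SAP 6.1.2 does not name Day 1 as a timepoint for the normalization frequency, and profiles do not correct a percentage in a table.

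The size is assumed, and zero is often the most likely count. P(none of 12) exceeds 50% in 14 of the 18 settings for total T3 and in 17 of 18 for free T4. In the full-SD truncated-normal settings, simulated entrants average about 7.9 to 8.1 nmol/L total T3 against the stated 7.2, so those settings deserve less weight. This stands.

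A reader might infer three stronger things that the documents do not support:

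- **That the 98% power or the T3/T4 efficacy criteria are compromised.** They concern the mean change from Day 1, which already uses each patient's own starting value.
- **That restricting the denominator gives 0% without a drug effect.** Patients above ULN on Day 1 can still drift below it through natural fluctuation and regression to the mean.
- **That an already-normal patient always inflates the result.** That patient must also be below ULN at the visit.

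**Conclusion.** The concern holds as a minor point of definition. The only written rule is a value below ULN, and neither the entry criterion nor the PD set ensures a raised Day 1 value. A patient already at or below ULN, or one below LLN, can therefore be counted as normalized.

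The plausible size is 0 to 1 of 12 patients per hormone, about 8 points for each such patient who remains below ULN. This rests on a baseline SD between half and all of the SD of change, and on the assumed distributions and correlations above. The reach is one descriptive proportion listed under the primary objective. The TSH exact test, the paired t-tests, the success criteria and the stated power are unchanged. It is an improvement the sponsor could make, not a flaw that threatens the study's conclusions. Confidence is medium, because the size depends on an assumed SD and the table shells could not be checked.

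**What to change.** In SAP 6.1.1, define normalization separately for each hormone: the denominator is patients above ULN at Day 1 predose, and the numerator is those whose value at the visit is within LLN to ULN. Report alongside it the number already at or below ULN on Day 1 and the number below LLN. Use the same rule for free T3 and total T4 wherever their normalization is shown. Leave the rescue rule in SAP section 4 as it is.

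If a common denominator is preferred, the minimum is to show the Day 1 count and the below-LLN count in the by-timepoint table or a footnote to it.

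The cost is one SAP sentence and a table shell or footnote. No new data are needed, since protocol Table 8-1 already schedules the hormones on Day 1 and Day 85. The drawback of the preferred version is a slightly smaller denominator (about 11 to 12 instead of 12) that differs between hormones and from TSH; the minimum version avoids this. Neither version supplies a control, so the report should still say that some normalization may occur without any drug effect.
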